## CL

Clearance (CL) is defined as the volume of plasma completely cleared of drug per unit time and is estimated in trials of an IV-administered drug as the dose divided by the  $AUC_{(0-\infty)}$ . It will be obtained from the **CL\_obs** parameter calculated by WinNonlin. If %AUCex is  $>20\%$  or the Lambda Z Acceptance Criteria are not met, the estimated CL value will be flagged when listed in the report and will be excluded from statistical summaries of parameter estimates and downstream calculations. CL will be reported in units of  $\text{L}/\text{h}/\text{kg}$ .

## $V_d$

Volume of distribution ( $V_d$ ) central is estimated in trials of an IV-administered drug as CL divided by  $\lambda z$ . It will be obtained from the **Vz\_obs** parameter calculated in WinNonlin. If %AUCex is  $>20\%$  or the Lambda Z Acceptance Criteria is not met, the estimated  $V_d$  value will be flagged when listed in the report and will be excluded from statistical summaries of parameter estimates and downstream calculations.  $V_d$  will be reported in units of  $\text{L}/\text{kg}$ .

## 11. IMMUNOGENICITY

Plasma samples for ADA measurements will be collected pre-infusion (60 to 0 minutes prior to start of infusion), Day  $56 \pm 4$ , Day  $112 \pm 7$ , Day  $150 \pm 7$ , and ET. For immunogenicity assays, baseline will be defined as the pre-infusion ADA measurement collected on Day 1. Unless otherwise specified, the immunogenicity population will be used when summarizing ADA results.

Positive and negative results for immunogenicity assays will be defined as described in [Section 4.5.3](#). ADA titers may be determined in the case of positive ADA results. Positive post-dose ADA results for participants with baseline ADA results will be further defined as treatment-induced ADA, treatment-boosted ADA, or pre-existing ADA, with the definitions of these provided in [Section 4.5.3](#).

The proportion of participants with a positive screening assay will be summarized by dose group and time point in [Table 34](#). The proportion of participants with negative, treatment-induced, treatment-boosted, and pre-existing ADA results will be summarized by dose group and post-dose time point in [Table 35](#). The incidence of ADA, defined as either treatment-induced or treatment-boosted ADA at any time point, will be summarized by dose group in [Table 36](#).

Reverse cumulative distribution (RCD) curves will be presented for post-dose ADA titers by dose group and time point in [Figure 11](#).

If positive ADA results are ascertained and ADA titers are determined, summary statistics of ADA titers including mean titer, SD, median titer, min titer, max titer, geometric mean titer (GMT), geometric mean fold rise (GMFR) from baseline, and percent of participants with at least a 4-fold rise in titer from baseline will be presented by dose group and time point in [Table 37](#). GMT, GMFR, and percent of participants with at least a 4-fold rise in titer from baseline will be presented with corresponding 95% confidence intervals. ADA GMTs will also be presented in [Figure 12](#) by dose group and time point.

Individual ADA assay results will be presented in [Listing 12](#).

### 11.1. ADA-Clearance Analysis

If five or more participants have positive ADA results, the effect of ADA incidence on the clearance of SAR440894 will be explored. The pharmacokinetics – immunogenicity subgroup population will be used for this analysis.

An analysis of variance (ANOVA) model will be fit to assess the effect of ADA on the clearance of SAR440894. The mixed effects model for the ANOVA analysis of the effect of ADA incidence on clearance of SAR440894 may be specified:

$$CL_{ijk} = \mu + a_{i(jk)} + \gamma_j + \beta_k + \epsilon_{ijk},$$

where  $CL$  represents clearance,  $\mu$  is the overall mean of clearance,  $a_{i(jk)}$  ( $i = 1, \dots, n_k$ ) is a random participant-specific intercept where there are  $n_k$  participants in the  $k$ th dose group in the pharmacokinetics – immunogenicity subset population with estimable clearance,  $\gamma_j$  ( $j = 1, 2$ ) represents the fixed ADA effect,  $\beta_k$  ( $k = 1, \dots, 5$ ) represents the fixed effect of dose group on clearance, and the errors  $\epsilon_{ijk}$  are assumed independent and identically distributed from the standard normal distribution. For this analysis, ADA will be defined as positive if a participant experiences either treatment-induced or treatment-boosted ADA at any time point, and ADA will be defined as negative if a participant does not experience treatment-induced or treatment-boosted ADA during the study period. Negative will be treated as the reference category. For this model, only participants in the pharmacokinetics-immunogenicity subgroup population with ADA results at

baseline will be included. Additionally, the association between dose group and clearance will be assessed, and dose group ( $\beta_k$ ) will only be included in the model if related to clearance.

The effect of ADA titers on clearance will additionally be explored via an analysis of covariance (ANCOVA) model, given:

$$CL_{ik} = \mu + a_{i(k)} + \gamma T_{ik} + \beta_k + \epsilon_{ik},$$

where  $CL$  represents clearance,  $\mu$  is the overall mean of clearance,  $a_{i(k)}$  ( $i = 1, \dots, n_k$ ) is a random participant-specific intercept where there are  $n_k$  participants in the  $k$ th dose group in the pharmacokinetics – immunogenicity subset population with estimable clearance,  $T_{ik}$  represents the value of the ADA titer for the  $i$ th participant in the  $k$ th dose group, and  $\gamma$  represents the change in clearance for a 1-unit increase in ADA titer,  $\beta_k$  ( $k = 1, \dots, 5$ ) represents the fixed effect of dose group on clearance, and the errors  $\epsilon_{ik}$  are assumed independent and identically distributed from the standard normal distribution. Again, dose group ( $\beta_k$ ) will only be included in the model if related to clearance.

For each mixed effects model, either clearance or log-transformed clearance,  $\log(CL)$ , will be used as the response. Whether clearance or log-transformed clearance will be included in the model will be determined after assessing normality and homogeneity of variance using Q-Q plots and plots of residuals against predicted values. The final models used will be stated in the CSR.

For the analysis of the effect of ADA incidence on clearance, the mean clearance will be presented for each ADA result along with the difference in mean clearance between positive and negative ADA, with 95% confidence intervals in **Table 38**. For the analysis of the effect of ADA titers on clearance, the ADA effect parameter estimates,  $\hat{\gamma}$ , will be presented with corresponding standard error and 95% confidence interval in **Table 39**. If the mixed effects models are fit on the log-transformed clearance, statistics and parameter estimates and 95% confidence intervals will be provided after their transformation from the log-transformed analysis back to the original scale for clearance.

The following pseudocode will be used to perform the ANOVA analysis for the effect of ADA incidence on clearance:

```
/* Fit Treatment Group-Specific Mixed-Effects ANOVA model */
proc mixed data=ada_clearance plots=studentpanel(marginal unpack);
class subjid ada(ref='Negative') trtn(ref='1');
model clearance = ada trt/ ddfm=kr2;
random intercept / subject=subjid;
estimate 'ADA Effect' ada 1 -1 / cl alpha=0.05; *use estimate statement to output mean difference;
ods output estimates=estimate_param; *output ADA mean difference estimate and CI;
run;

/* If Diagnostics Indicate Log-transformed Clearance is More Appropriate*/
/* Fit Treatment Group-Specific Mixed-Effects ANOVA model for log-transformed clearance */
proc mixed data=ada_clearance plots=studentpanel(marginal unpack);
class subjid ada(ref='Negative') trt(ref='1');
model logclearance = ada trt / ddfm=kr2;
random intercept / subject=subjid;
estimate 'ADA Effect' ada 1 -1 / cl alpha=0.05; *use estimate statement to output log-transformed mean difference;
ods output estimates=estimate_logparam; *output log-transformed mean difference and CI;
run;

/* Transform mean difference estimate and CI limits to original scale (similar for mean clearance) */
```

```
data estimate_logparam; set estimate_logparam;
OG_est=exp(estimate);
OG_lower=exp(lower);
OG_upper=exp(upper);
run;
```

The following pseudocode will be used to perform the ANCOVA analysis for the effect of ADA titer on clearance:

```
/* Fit Treatment Group-Specific Mixed-Effects ANCOVA model */
proc mixed data=ada_clearance plots=studentpanel(marginal unpack);
class subjid trt(ref='1');
model clearance = ada trt/ ddfm=kr2;
random intercept / subject=subjid;
estimate 'ADA Effect' ada 1 -1 / cl alpha=0.05; *use estimate statement to output ADA parameter estimate;
ods output estimates=estimate_param; *output ADA parameter estimate and CI;
run;

/* If Diagnostics Indicate Log-transformed Clearance is More Appropriate*/
/* Fit Treatment Group-Specific Mixed-Effects ANCOVA model for log-transformed clearance */
proc mixed data=ada_clearance plots=studentpanel(marginal unpack);
class subjid trt(ref='1');
model logclearance = ada trt / ddfm=kr2;
random intercept / subject=subjid;
estimate 'ADA Effect' ada 1 -1 / cl alpha=0.05; *use estimate statement to output log-transformed ADA parameter estimate;
ods output estimates=estimate_logparam; *output log-transformed ADA parameter estimate and CI;
run;

/* Transform parameter estimate and CI limits to original scale */
data estimate_logparam; set estimate_logparam;
OG_est=exp(estimate);
OG_lower=exp(lower);
OG_upper=exp(upper);
run;
```

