## 4. INVESTIGATIONAL PLAN

### 4.1. Overall Study Design and Plan

This is a Phase 1, randomized, double-blind, placebo-controlled, multi-site, single dose escalation study to evaluate the safety, PK, and immunogenicity of 5 dose levels of IV SAR440894 vs placebo in healthy adults. An overall schematic of the study design is given in [Figure 1](#). The study is expected to enroll approximately 40 participants into 5 cohorts of 8 participants each.

Study enrollment will proceed from Cohort 1 to Cohort 5 starting with the lowest dose and escalating to the next higher dose. In each of the 5 cohorts, participants will be randomized to either SAR440894 (n=6) or placebo (n=2) in an overall 3:1 ratio ([Table 1](#)). In each cohort, 2 sentinel participants will first be randomized to receive SAR440894 or placebo in a 1:1 ratio. The enrolling site principal investigator(s) (PI(s)) will review safety data through Day 4 to confirm no halting criteria are met. After confirmation that sentinel participant halting rules have not been met, the remaining 6 participants in each cohort will be randomized in a 5:1 ratio to SAR440894 and placebo and dosed in pairs of two at least 24 hours apart. Dosing start times will be staggered by at least 15 minutes between participants. Participants will remain in confinement for at least 72 hours after receiving study product. Thereafter, follow-up in each cohort will occur until Day 150 ( $\pm 7$  days) to account for the long half-life of SAR440894 and allow for appropriate characterization of the PK, safety, and immunogenicity of SAR440894.

Blood (plasma) samples will be collected for measuring SAR440894 concentrations for PK analysis at baseline pre-infusion and for 72 hours following the end of infusion. Additional plasma samples will be collected on Day  $7 \pm 1$ , Day  $14 \pm 2$ , Day  $28 \pm 4$ , Day  $56 \pm 4$ , Day  $84 \pm 7$ , Day  $112 \pm 7$ , Day  $150 \pm 7$ , and ET (if needed). Blood (plasma) samples for ADA measurements will be collected for assessing the immunogenicity of SAR440894 at baseline pre-infusion and on Day  $56 \pm 4$ , Day  $112 \pm 7$ , Day  $150 \pm 7$ , and ET. PK and immunogenicity plasma samples will be analyzed by Aptuit (Verona) Srl.

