## **4.4. Treatments**

### **4.4.1. Treatments Administered**

In each cohort, participants will be randomized to SAR440894 or placebo. SAR440894 or placebo will be administered as a single IV infusion over 60 minutes (with an acceptable range of 55 to 70 minutes). For each successive treatment cohort, the dose of SAR440894 will be progressively escalated from 0.3 mg/kg in Cohort 1 to 1 mg/kg in Cohort 2 to 3 mg/kg in Cohort 3 to 10 mg/kg in Cohort 4 to 20 mg/kg in Cohort 5.

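### SAP 11.1: with one clearance per participant the random intercept is redundant, the error variance is misstated as 1, and the trigger for the ADA-incidence model does not match that model's ADA-positive group

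*SAP*

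**What the plan says.** **Models.** SAP 11.1 specifies an ANOVA of CL on ADA incidence (Table 38) and an ANCOVA of CL on ADA titer (Table 39). Either CL or log CL is the response, chosen from residual plots, and dose group is kept only if related to CL. In both models the participant term "is a random participant-specific intercept where there are" n_k participants in dose group k, and in both the errors "are assumed independent and identically distributed from the standard normal distribution". The SAP commits to the pseudocode it prints. That code has four PROC MIXED blocks; each contains "random intercept / subject=subjid" and requests ddfm=kr2. None fixes the residual variance.

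**Response.** SAP 4.4.1: "SAR440894 or placebo will be administered as a single IV infusion over 60 minutes". Under SAP 10.2, CL "is estimated in trials of an IV-administered drug as the dose divided by the" AUC to infinity. If more than 20% of that AUC is extrapolated, or the terminal slope fails its criteria, CL "will be excluded from statistical summaries of parameter estimates and downstream calculations". In each of five cohorts "participants will be randomized to either SAR440894 (n=6) or placebo (n=2) in an overall 3:1 ratio" (SAP 4.1).

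**Trigger.** SAP 11.1: "If five or more participants have positive ADA results, the effect of ADA incidence on the clearance of SAR440894 will be explored". SAP 4.5.3 defines a positive result as one that is positive on both screening and confirmation, with no limit on arm, time point or ADA class. The sentence after the trigger names the PK-immunogenicity population for the analysis. The ANOVA's positive group is treatment-induced or treatment-boosted ADA only, among participants with a baseline ADA result. Protocol 10.5.3 uses the same count of five, but permits the analysis where the SAP commits to it.

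**The concern.** A participant random intercept represents what repeated measurements on one person share. Here there are no repeats, so it duplicates the residual. The planned fit then has two variance parameters where the data carry information on one, together with a degrees-of-freedom method that has to invert the information matrix for both.

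The text and the code also describe different models: variance fixed at 1 in the text, variance estimated in the code. Someone reproducing Tables 38 and 39 from the text would not get the coded intervals.

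Finally, the rule that starts the analysis and the group that the ANOVA compares are defined differently. At worst, the rule is met and there is no ADA-positive participant to compare.

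**Working it through.** The plan gives no sample size, power or precision figure for this analysis, so there is none to reproduce.

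**Inputs**
- CL values per participant: 1 (SAP 4.4.1, 10.2). Participants who can have a CL: at most 5 × 6 = 30 (SAP 4.1).
- Animal CL (Protocol 2.1): monkey 0.002 L/day/kg, mouse 0.005 L/day/kg. No human value is given.
- Assumptions: between-participant CV of CL 20%, 30% or 40%; 5 of 30 ADA-positive, one per dose group.

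**1. Can the two variances be separated?** With one observation each, V = s2_a·I + s2_e·I = (s2_a + s2_e)·I. The derivative of V is I for both parameters, so every entry of the 2×2 REML information matrix equals ½·tr(PP), where P is the REML projection matrix. The determinant is 0 and the rank is 1.

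Check on one simulated data set of 30 log CL values (CV 30%, dose in the model):
- The REML log-likelihood is -4.966042 whether the intercept takes 0, 25, 50, 75 or 100% of the variance.
- All four information entries are 3635.42.
- At every split the ADA estimate is 0.523, SE 0.117, 95% CI on 24 df 0.281 to 0.765, the same as least squares.

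The same invariance appears at CV 20% and 40%. A trial mixed-model fit of other simulated data, in a package other than SAS, split the variance arbitrarily (0.045 + 0.045, summing to the least-squares 0.090). It warned that the Hessian was not positive definite and returned an SE of 0 for the ADA effect, against 0.147 by least squares. SAS was not run.

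**2. What does the ordinary model give?** Within one dose group, 1 positive against 5 negatives has variance s2·(1 + 1/5) = 1.2·s2. Averaged over five groups this is 1.2·s2/5 = 0.24·s2, so SE = 0.490·s on 30 − 6 = 24 df (t = 2.064). On log CL, s = sqrt(ln(1 + CV²)), and the ratio interval is the estimate times or divided by exp(2.064 × 0.490 × s):

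| CV (assumed) | s | Factor | Simulated coverage (20,000 runs) |
|---|---|---|---|
| 20% | 0.198 | 1.22 | 95.2% |
| 30% | 0.294 | 1.35 | 95.1% |
| 40% | 0.385 | 1.48 | 94.9% |

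**3. What does variance 1 mean?** The half-width is 1.96 × 0.490 = 0.960. On log CL the factor is exp(0.960) = 2.61, with coverage of about 100%. On CL it is 0.960 L/h/kg. Animal CL is 0.002/24 = 0.0000833 (monkey) or 0.005/24 = 0.000208 L/h/kg (mouse), so the half-width would be about 11,500 or 4,600 times CL. The code does not impose this.

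**4. Who counts toward five, and who is ADA-positive in the ANOVA?**

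| Participant with a confirmed positive | Counts toward five | ADA-positive in ANOVA |
|---|---|---|
| Placebo | Yes, unless the trigger is limited to the PK-immunogenicity population | No: no CL |
| Active, pre-existing ADA | Yes | No: ADA-negative |
| Active, positive at baseline only | Yes | No: ADA-negative |
| Active, no baseline ADA result | Yes | No: left out |
| Active, CL excluded | Yes (the Table 8 shell asks for any one PK parameter) | No |
| Active, induced or boosted, with baseline ADA and estimable CL | Yes | Yes |

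Five can therefore be reached with none in the last row.

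Half-width of the ADA contrast for 30 participants:
- Without dose (28 df, t = 2.048): 2.048 × sqrt(1 + 1/29) = 2.08 SD with one positive; 2.048 × sqrt(1/5 + 1/25) = 1.00 SD with five.
- With dose (24 df): 2.064 × sqrt(1 + 1/5) = 2.26 SD with one; 2.064 × 0.490 = 1.01 SD with five.
- With no positive, the contrast cannot be estimated.

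Illustration for placebo under the literal trigger: if five positives fell at random among 40 participants, all five would be on active in C(30,5)/C(40,5) = 142,506/658,008 = 22% of cases.

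**The case against.** The strongest reply is that little of this would change a reported number. A redundant intercept leaves the ADA estimate and its least-squares interval as they are. The code estimates the residual variance, the SAP requires residual diagnostics, and the final models are to be stated in the study report. The analysis is conditional and exploratory, with no hypothesis tests planned. Table 38 prints N for each ADA group, so a thin comparison would be visible. All of this stands, and it limits the weight of the point.

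Four stronger readings are tempting and should not be drawn:

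- *The variance and intervals are undefined.* Only the split into two components is. Their sum and the least-squares interval are defined, as step 1 shows.
- *The Kenward-Roger fit will fail.* The matrix it must invert is singular, but the planned software was not tested. The supportable statement is that its output is not assured.
- *The reported intervals will be thousands of times too wide.* That follows the sentence on the errors, not the code to be run, and it borrows animal clearance for humans.
- *The trigger plainly counts placebo recipients.* The next sentence names a population confined to complete SAR440894 doses, so a narrower reading is reasonable. The trigger also speaks of ADA incidence, which SAP Section 11 defines as induced or boosted. But the count itself is of positive results, a separately defined term. Even within that population, pre-existing and baseline-only positives count toward five and are ADA-negative in the ANOVA.

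One objection changes the remedy. The titer ANCOVA has no ADA-positive group and can use any positive titer, including pre-existing ADA. A single trigger requiring induced or boosted ADA would suppress it for no reason.

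**Conclusion.** The point holds in three parts.

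1. The participant intercept is redundant in both models and all four code blocks. The information matrix for the two variances has rank 1, so the coded Kenward-Roger interval is not assured. This is algebra and needs no assumption about CL.
2. The standard normal statement is wrong for CL in L/h/kg or log CL and contradicts the code. On log CL the literal factor is 2.61, against 1.22 to 1.48 under the assumed CV of 20% to 40% and five positives among 30. It is an error in the text, not a forecast of the output.
3. The trigger and the incidence ANOVA use different definitions, so the ANOVA can be started with one ADA-positive participant (about twice the half-width of five) or none. How likely this is cannot be judged from the documents, which give no expected ADA rate.

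This should be corrected before the analysis is run. It bears on exploratory Tables 38 and 39 only, not on the primary safety endpoints.

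**What to change.** - Delete the participant intercept from both model equations and the RANDOM statement from all four code blocks. State the errors as N(0, sigma²) with sigma² estimated. Fit ordinary fixed-effects ANOVA and ANCOVA with t intervals on n − p degrees of freedom; the Kenward-Roger option then has no purpose.
- Incidence ANOVA: require at least five SAR440894 recipients with treatment-induced or treatment-boosted ADA, a baseline ADA result and an estimable CL.
- Titer ANCOVA: keep a trigger on positive titers, counted among SAR440894 recipients with estimable CL.
- Record the departure from the Protocol 10.5.3 wording in SAP Section 15.
- In the same edit, correct two further slips that deleting the RANDOM line would leave. The first ANOVA block names trtn in CLASS but trt in MODEL. The ANCOVA blocks leave ada out of CLASS yet give it two coefficients in ESTIMATE.

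The cost is SAP text and a few lines of code, with no change to data collection. The downside is that the incidence model will be run slightly less often.

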## 2. INTRODUCTION

This is a Phase 1, randomized, double-blind, placebo-controlled, multi-site, single dose escalation study to evaluate the safety, PK, and immunogenicity of intravenous (IV) SAR440894 in healthy adult participants. Five cohorts of 8 participants each will be enrolled in the study. In each of the 5 cohorts, 6 participants will be randomized to SAR440894, and 2 participants will be randomized to placebo. Each cohort will complete the study approximately 22 weeks (150 days) from randomization through Follow-up, which accounts for the long half-life of SAR440894 and will allow for appropriate characterization of the safety, PK, and immunogenicity of SAR440894.

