**Table 38: ADA Incidence – Clearance Analysis Results – Pharmacokinetics – Immunogenicity Subset**

[Implementation Note: If  $\log(CL)$  is used in the ANOVA model, statistics will be provided after exponentiation to the original units for clearance and the third footnote will be updated to “*Statistics are provided on the original scale for CL, after being obtained using a mixed effects ANOVA model for  $\log(CL)$  with fixed covariates for Dose Group and ADA Result, using Negative ADA as the reference group.*”]

If Dose Group is deemed unrelated to clearance and is excluded from the model, the third footnote will be updated to indicate the only fixed covariate in the model was ADA Result.]

Statistic	ADA Incidence Group	
	ADA Positive	ADA Negative
N	x	x
Mean Clearance	x.xx	x.xx
Mean Clearance 95% CI	(x.xx, x.xx)	(x.xx, x.xx)
Difference in Mean Clearance (Positive – Negative)	x.xx	-
Difference in Mean Clearance 95% CI	(x.xx, x.xx)	-

Notes: N = Number of participants in the Pharmacokinetics – Immunogenicity Subset with estimable clearance (CL), excluding those for whom treatment-induced and treatment-boosted ADA cannot be assessed.  
 For this analysis, Positive ADA is defined as experiencing either treatment-induced or treatment-boosted ADA at any time point, and Negative ADA will be defined as not experiencing treatment-induced or treatment-boosted ADA during the study period.  
 Statistics are obtained using a mixed effects ANOVA model for CL with fixed covariates for Dose Group and ADA Result, using Negative ADA as the reference group.

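### SAP 11.1 lets dose group be dropped from the ADA-clearance models after an unspecified look at the same data, while its code always keeps it; dropping dose can bias the ADA effect if ADA incidence also varies with dose

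*SAP*

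**What the plan says.** SAP 11.1 plans two models for clearance (CL): an ANOVA on ADA incidence and an ANCOVA on ADA titer. Both model equations contain a fixed dose-group effect with five levels. For the first, the text adds that "the association between dose group and clearance will be assessed" and that dose group "will only be included in the model if related to clearance"; the same condition is repeated for the second. The shells carry the option through: the implementation note to Table 38 begins "If Dose Group is deemed unrelated to clearance and is excluded from the model", and Table 39 has a matching note.

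The analysis is triggered "If five or more participants have positive ADA results". Table 38 reports "the difference in mean clearance between positive and negative ADA, with 95% confidence intervals". The response is "either clearance or log-transformed clearance", also chosen after looking at the data. The final models are to be stated in the CSR.

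The pseudocode in the same section has four model fits (two models, each on the original and the log scale). Each MODEL statement contains the ADA term and the treatment term, and no selection step is coded.

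**The concern.** Two things are wrong with the rule as written.

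First, text and code do not describe the same analysis. A programmer following the prose and one following the pseudocode could report different ADA effects from the same data.

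Secondly, the prose makes adjustment for dose depend on an apparent relation with the outcome in a very small sample. It does not say how the relation is to be judged, at what level, or whether before or after allowing for ADA. With so few participants per dose, failing to see a relation is weak evidence that there is none. If dose is dropped although clearance does vary with dose, and ADA positivity varies with dose too, part of the dose effect is attributed to ADA. The interval is then calculated as if the model had been fixed in advance. The estimates at stake are those in Tables 38 and 39.

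**Working it through.** **Inputs from the documents.** "In each of the 5 cohorts, 6 participants will be randomized to SAR440894, and 2 participants will be randomized to placebo" (SAP 2), so at most 5 × 6 = 30 participants have a clearance value. There can be fewer: under CL in SAP 10.2, values with more than 20% extrapolated AUC or a failed Lambda Z criterion "will be excluded from statistical summaries of parameter estimates and downstream calculations". The plan states no power or coverage figure for this analysis, so there is nothing to reproduce.

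**Inputs assumed.** The documents give no between-subject CV of clearance, dose effect on clearance, ADA rate by dose or selection threshold. These are varied below. Each participant has one clearance value, so the random intercept cannot be separated from the error, and ordinary linear models on log CL were used.

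**Step 1: how often a dose test misses a real relation.** Take a one-way F-test with 4 and 25 df at 0.05. Let log clearance change evenly across the five groups, with lowest-to-highest ratio R. With σ² = ln(1 + CV²), the noncentrality is λ = n Σ(μₖ − μ̄)²/σ² = n × 0.625 × (ln R)²/σ².

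For R = 1.5, CV = 30%, n = 6: λ = 6 × 0.625 × 0.1644/0.0862 = 7.15, and the test misses in 53% of trials.

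| R | CV 20% | CV 25% | CV 30% | CV 40% |
|---|---|---|---|---|
| 1.25 | 68% | 79% | 84% | 89% |
| 1.5 | 16% | 37% | 53% | 72% |
| 2.0 | 0% | 1% | 7% | 28% |

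Misses exceed one half only when R is below about 1.33, 1.42, 1.52 and 1.74 respectively.

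**Step 2: bias if dose is dropped.** Assume clearance 35/20/5/0/0% higher and ADA rates 60/40/20/10/5% from lowest to highest dose, with no true ADA effect. The log shifts are 0.300, 0.182, 0.049, 0, 0.
- Mean shift in ADA-positives: (0.6 × 0.300 + 0.4 × 0.182 + 0.2 × 0.049)/1.35 = 0.195.
- Mean shift in ADA-negatives: (0.4 × 0.300 + 0.6 × 0.182 + 0.8 × 0.049)/3.65 = 0.074.
- Spurious ADA effect with dose never in the model: 0.195 − 0.074 = 0.121 on the log scale.

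**Step 3: the whole procedure.** Simulation: 8,000 trials per setting, 6 per dose, at least five ADA-positive, residual SD 0.3, true ADA effect zero. Unless stated otherwise, dose is kept if the unadjusted test gives p < 0.05.

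| Setting | Bias (log CL) | Coverage |
|---|---|---|
| Step 2 scenario (dose kept in 31% of trials) | 0.071 to 0.073 | 90.3% to 90.7% |
| Same, threshold 0.10 | – | 92% to 93% |
| Same, dose tested after allowing for ADA | – | 86.4% |
| Same, dose group always in | 0.001 | 94.9% |
| Same clearance pattern, equal ADA rates | 0.004 | about 95% |
| Same clearance pattern, ADA 35% to 20% | 0.022 | about 94.5% |
| Flat clearance, ADA 60% to 5% | – | 95% |

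The bias is below 0.69 × 0.121 = 0.083 because dose is dropped mainly in trials where its observed effect happens to be small. On the ratio scale, exp(0.072) = 1.07.

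**Step 4: wider grid.** CV was varied from 20% to 40% and R from 1.25 to 2. Coverage after selection:

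| ADA rate, lowest to highest dose | Dose test ignores ADA | Dose test adjusts for ADA |
|---|---|---|
| 70% to 5% | 89.9% to 95.3% | 79.6% to 93.6% |
| 50% to 10% | 92.9% to 94.7% | 89.5% to 94.8% |
| 30% throughout | 94.9% to 95.2% | 93.8% to 94.9% |

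With dose group always in, coverage was 94.4% to 95.5% in every setting and the ADA ratio was between 0.996 and 1.004.

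**The case against.** The harm needs two conditions at once, and the documents do not predict either. The protocol notes that the antibody has no human target, and it excludes people with CHIKV antibodies or serologically proven exposure. It reports a low likelihood of immunogenicity from cell assays and no ADA in animals. The scenario's ADA rates average 1.35/5 = 27%, about 8 of 30, and the trigger of five may never be reached. The analysis is exploratory (the protocol says only that it may be done), SAP 6.8 plans no hypothesis tests, and the CSR and the shell footnote would disclose that dose was dropped. All of this stands, and it keeps the point minor. It does not justify the rule: neither link can be ruled out beforehand, the SAP's own model contains a dose effect, and disclosure does not restore coverage.

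Three stronger readings are tempting and are not supported.
- That the rule usually misses a real relation. This is true only of modest relations; a 2-fold relation is found in 72% to 100% of trials. The SAP also speaks only of assessing the relation, so the F-test and its level are assumptions.
- That Table 38's intervals lack 95% coverage in general. Clear under-coverage requires both links. A doubled false-positive rate would have no planned test attached to it.
- That one log(dose) term should replace dose group. In the Step 2 scenario it does well (bias about 0.012, coverage 94.8%). If clearance is 2-fold higher at the lowest dose only, it gives bias 0.043 to 0.044 and coverage of 93.1% to 93.4%. The SAP's conditional rule does better there: it keeps dose in 97% of trials, with bias 0.010 and coverage 95.0%.

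**Conclusion.** The concern holds in conditional form. The conflict between text and code needs no assumption. The statistical harm does: selecting dose on an unstated criterion can miss a modest dose-clearance relation, and where ADA incidence also varies steeply with dose the ADA effect is biased and its interval too narrow. In the worked scenario that is about +7% in clearance and coverage of about 90% to 91%. Coverage was as low as about 80% in the grid when the unstated check was taken to be ADA-adjusted. Coverage is about 94% to 95% when ADA is unrelated to dose or clearance is flat. The size rests entirely on assumed CVs, dose effects, ADA rates and thresholds. The titer model carries the same rule but was not simulated. Severity is low: this is a triggered, exploratory secondary analysis.

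**What to change.** In SAP 11.1, delete the sentences that make dose group conditional in both models, together with the matching implementation notes to Tables 38 and 39. State that dose group is always included, as the model equations and pseudocode already have it. While editing, make the dose variable's name agree between CLASS and MODEL in the first pseudocode block, which uses trtn in one and trt in the other. The unadjusted result, or a version with log(dose), can be shown as a sensitivity analysis.

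The change is to wording. The price is precision when adjustment was not needed. With flat clearance and ADA rates of 60% to 5%, the average interval width on log CL was 0.510 under the conditional rule and 0.634 with dose group always in: 0.634/0.510 = 1.24, about 24% wider. With log(dose) it was 0.587, about 15% wider, but that model carries the misspecification risk described above.
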